6. SPECIFIC AIMS

Primary aim:

To compare the mean pain score at the time of osmotic dilator insertion among women randomized to a 1% lidocaine and buprenorphine paracervical block compared to a 1% lidocaine paracervical block alone.

We hypothesize that in patients undergoing osmotic dilator insertion in preparation for dilation and evacuation, the addition of buprenorphine 0.15mg to a 1% lidocaine paracervical block will be associated with lower mean pain scores at time of osmotic dilator insertion compared to women who receive a 1% lidocaine paracervical block alone.

Secondary aims:

1. To compare the mean pain score 2 hours after osmotic dilator insertion among women randomized to a lidocaine and buprenorphine paracervical block compared to a lidocaine paracervical block alone.
2. To assess overall narcotic and ibuprofen use after osmotic dilator placement and before dilation and evacuation procedure.
3. To assess opioid related side effects.
4. To determine patient satisfaction with pain control during and after osmotic dilator insertion.

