9. RESEARCH DESIGN AND METHODS

This is a randomized, 2-arm (1:1), double blinded clinical trial comparing pain scores at the time of osmotic dilator insertion and at specific points after insertion with a buprenorphine plus 1% lidocaine paracervical block compared to a paracervical block alone in women who have osmotic cervical dilators placed.

Primary Hypothesis:

In patients undergoing osmotic dilator insertion in preparation for dilation and evacuation, the addition of buprenorphine 0.15mg to a 1% lidocaine paracervical block will be associated with lower mean pain scores at time of osmotic dilator insertion compared to women who receive a 1% lidocaine paracervical block alone.

Secondary hypotheses:

In patients undergoing osmotic dilator insertion in preparation for dilation and evacuation, the addition of buprenorphine 0.15mg to a 1% lidocaine paracervical block will be associated with lower mean pain scores 2 hours after osmotic dilator insertion compared to women who receive a 1% lidocaine paracervical block alone.

In order to investigate this hypothesis, the following study design is proposed:

We plan to recruit at two study sites – the University of California, San Diego (UCSD) and Planned Parenthood of the Pacific Southwest (PPPSW). The UCSD study team will be responsible for all study procedures conducted at Planned Parenthood. Members of the UCSD study team will be determining eligibility, consenting patients, administering patient questionnaires, collecting data, and performing data analysis. Planned Parenthood clinicians will be administering the study medication during the procedure and will not be involved in any other research procedures.

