The table below indicates the time point at which the various assessments will be performed. Assessments will be performed over one to two days: on the day of osmotic dilator insertion and on the day of D&E. If same day dilators are used, the final assessment will be performed immediately prior to D&E. Overall, the process of clinician evaluation, procedural consent, study recruitment, study consent, performance of procedure, and immediate post-procedure questionnaire should take about 30 minutes. The follow up questionnaires and questionnaire prior to D&E will take about 10 minutes. Participants will receive a questionnaire sent via text message link at 1 hour, 2 hours, and 6 hours post-procedure. This questionnaire

assesses the need for oral analgesics for pain as well as participant satisfaction with their pain control at that study point. Participants will take a questionnaire on the morning of D&E asking them to rate their current pain and to recall their maximum pain score over the preceding day and their overall satisfaction with their pain control. The need for follow up will be determined per usual clinician practice and preference.

Randomization:

Block randomization will be performed in alternating blocks of 4 and 6 stratified by vaginal parity (vaginally nulliparous versus vaginally multiparous). The study team member will open the designated sealed sequentially numbered opaque randomization envelope containing computer generated randomization code of the type of paracervical block and hand it to the clinician performing the procedure. A clinician who will not be administering the paracervical block will then open the envelope and prepare the designated paracervical block into two 10 mL syringes. A different clinician blinded to the treatment group will perform the standardized procedure for osmotic dilator insertion using a speculum, 25-gauge spinal needle to inject the paracervical block, Dennison dilators to dilate the cervix if that is the clinician's practice, and insertion of laminaria and/or Dilapan-S. The amount of time it takes to inject the paracervical block will be recorded.

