Intervention: A paracervical block with 20mL of 1% buffered lidocaine plus 0.15mg of buprenorphine will be injected prior to osmotic dilator insertion. A paracervical block with 20mL of 1% buffered lidocaine will be used in the control group. The patient will not be charged for the study drug. All drug costs will be covered by the study (this is also stated in the consent form).

Outcomes:

- 1) Sociodemographic and clinical data:** age, race, ethnicity, level of education, marital status, height, weight, obstetric history, history of cervical procedures (e.g. LEEP procedure or Conization), chronic baseline pain
- 2) Primary outcome:** Level of pain as rated on an 11-point (0-10) numeric rating scale during osmotic dilator insertion.
- 3) Secondary outcomes:**
 - a. Pain (Numeric Rating Scale):
 - i. Baseline (before procedure)
 - ii. Paracervical block placement
 - iii. 5 minutes post procedure
 - iv. 1 hour post procedure
 - v. 2 hours post procedure
 - vi. 6 hours post-procedure
 - b. Satisfaction
 - i. Likert scale questions
 1. How satisfied are you with the amount of pain control that you had during the procedure?
 2. If you had to have these dilators placed for a procedure in the future, would you choose to have the same pain medication that you received today?
 - c. Adverse events – side effects at time of paracervical block placement and after procedure
 - d. Survey of provider (resident, fellow, attending, advance practice clinician) performing procedure
 - i. Number of dilators placed

- ii. Ease of osmotic dilator placement
- iii. If patient will return for second set of dilators
- iv. Major complications
- v. Type of clinician (resident, attending, advance practice clinician)

No specimens will be collected for research purposes. All research data will be collected on electronic tablets and de-identified via REDCap.

Power Calculation:

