It is suggested that a 2-point reduction in pain on the numeric rating scale (NRS) is clinically meaningful.²⁴⁻²⁷ No existing study parallels the outcomes of our proposed research (pain at time of osmotic dilator insertion using the numeric rating scale). One previous study used the Visual Analog Scale (a 0-100mm linear scale) to compare pain at the time of osmotic dilator insertion between a 1% lidocaine paracervical block and vaginal lidocaine gel.⁸ The visual analog scale and the numeric rating scale have modest correlation.⁴² The median pain score during osmotic dilator insertion in the 1% lidocaine paracervical block group was 61 (which correlates to 6 on the numeric rating scale) with a range from 0-100.

In order to detect a 2-point difference on the NRS at the time of osmotic dilator insertion with 80% power and a two-sided alpha of 0.05, we will need a total of 52 patients in each study arm (26 per arm). We plan to stratify the groups by vaginal parity (nulliparous versus multiparous) as vaginal parity may affect pain at the time of osmotic dilator insertion. In order to stratify by vaginal parity, we will need a total of 104 women (52 in each strata) to see a difference between strata per group. We plan to enroll an additional 10% to account for protocol deviation and participant dropout for a total of 114 participants. With a one to one randomization allocation, approximately half will be randomized to receive a paracervical block with buprenorphine and 1% lidocaine and half will receive a paracervical block with 1% lidocaine alone. Additionally, randomization will be stratified by vaginal parity (vaginally nulliparous versus vaginally multiparous).

Data Analysis

The baseline participant survey, NRS scores, side effects, and post-procedure participant and provider surveys will be performed by the study coordinator using REDCap loaded on to an electronic tablet. This data will be transferred to a spreadsheet in SPSS. Bivariate comparisons will be analyzed using chi squared test or Fisher’s Exact test for categorical variables and t-test or Mann-Whitney for continuous variables depending on the distribution of the data as appropriate. The primary outcomes will be evaluated per intent-to-treat analysis.

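### The increase to 104 women is justified by parity stratification and a by-parity difference, but stratified randomization needs no increase and no planned analysis uses a by-parity contrast

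*Combined protocol and SAP*

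**What the plan says.** All of the sizing is in Section 9, Power Calculation. The target is a 2-point difference on the 0-10 scale, with 80% power and two-sided alpha 0.05. The sentence giving the base number contradicts itself: it presents 52 as a total, then as the number in each arm, then adds 26 per arm in brackets. No SD is stated.

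The reason for stratifying is given "as vaginal parity may affect pain at the time of osmotic dilator insertion". The text continues that, for this stratification, "we will need a total of 104 women (52 in each strata) to see a difference between strata per group". Then: "We plan to enroll an additional 10% to account for protocol deviation and participant dropout for a total of 114 participants".

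Under Randomization in the same section, "Block randomization will be performed in alternating blocks of 4 and 6 stratified by vaginal parity". No quota or cap on stratum size is given.

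The rest of the plan compares the two blocks overall:

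- Section 6, primary aim: "To compare the mean pain score at the time of osmotic dilator insertion among women randomized" to the two blocks.
- Section 9, primary hypothesis: the buprenorphine block "will be associated with lower mean pain scores at time of osmotic dilator insertion".
- Section 9, primary outcome: "Level of pain as rated on an 11-point (0-10) numeric rating scale during osmotic dilator insertion".
- Section 9, Data Analysis: bivariate tests and an intention-to-treat statement, with no parity term.

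**The concern.** The sentence that takes the sample to 104 gives two reasons, and neither holds as written.

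The first is stratification itself. A factor that may affect pain is a reason to balance the arms on it. Permuted blocks within parity strata do that whether 52 or 104 women are enrolled.

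The second is a by-parity inference, which the text does not define. It could mean the treatment effect within each stratum, a difference between strata in the treatment effect, or a comparison of nulliparous with multiparous women within each arm. These are different questions, and 104 women do not serve them equally. None is carried into the aims or the analysis.

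What is at stake is interpretation. If results by parity are reported, they will be unplanned, yet the sample-size section will read as though the trial had been sized for them.

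**Working it through.** **1. The plan's own sums.** 2 × 26 = 52; 2 × 52 = 104; 104 × 1.10 = 114.4, reported as 114. These reproduce.

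**2. Which 52?** Inputs from the Power Calculation: difference 2, power 80%, two-sided alpha 0.05. For a two-sample t-test with n per arm, power comes from the noncentral t with 2n − 2 degrees of freedom and noncentrality 2 / (SD × √(2/n)). Solving for the SD that gives 80% power:

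- 26 per arm: SD = 2.52
- 52 per arm: SD = 3.6

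Without a stated SD, power alone cannot settle the reading. The bracketed 26 per arm and the later 52 per stratum both fit 52 as the total. SD 2.5 is therefore used below, as an assumption.

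**3. Pooled primary comparison, 52 v 52.** SE = 2.5 × √(2/52) = 0.490; 2 / 0.490 = 4.08; df 102; power 98%.

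**4. If the purpose is the treatment effect within each stratum.** At an even split there are 26 v 26: SE = 2.5 × √(2/26) = 0.693; 2 / 0.693 = 2.88; df 50; power 81%. The documents give no parity mix, so the other splits are illustrative.

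| Parity split | Smaller stratum, 104 evaluable | Smaller stratum, 114 evaluable |
|---|---|---|
| 50/50 | 26.0 per arm, 81% | 28.5 per arm, 84% |
| 45/55 | 23.4 per arm, 76% | 25.65 per arm, 80% |
| 40/60 | 20.8 per arm, 71% | 22.8 per arm, 75% |

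**5. If the purpose is a difference between strata in the treatment effect.** With 26 women in each of four cells, SE = SD × √(4/26), df 100, and a true interaction of 2 points:

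| SD | SE | 2 / SE | Power |
|---|---|---|---|
| 2.0 | 0.784 | 2.55 | 71% |
| 2.5 | 0.981 | 2.04 | 52% |
| 3.0 | 1.177 | 1.70 | 39% |

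At SD 2.5, 80% power needs about 50 per cell, or 200 women.

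**6. If the purpose is parity compared within each arm.** This is again 26 v 26, so about 81% for 2 points at an even split, but it says nothing about buprenorphine.

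**7. If 52 per arm was meant.** Then 104 is the ordinary two-arm total. At SD 3.6, power is 80% pooled (52 v 52) but only 50% within a 52-woman stratum (26 v 26). For a 2-point interaction, SE = 3.6 × √(4/26) = 1.412, 2 / 1.412 = 1.42, and power is 29%. The by-parity claim would be weaker still.

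**The case against.** **A by-parity purpose is stated.** This is true. The plan does not claim only that stratification needs 104 women, and repeating 26 per arm in each stratum makes within-stratum power the likeliest intent. It would be unfair to say that the sample was doubled merely to stratify. What remains is that the purpose is ambiguous and is not carried into any aim or analysis.

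**Nothing may have been doubled.** If 52 per arm was meant, 104 is simply the two-arm total. The wording allows this, so the doubling is the likelier reading and not a settled fact. On either reading, the sentence tying 104 to stratification is wrong.

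**Uneven strata cost little.** This stands in part. The loss is gradual: a 45/55 split with all 114 women evaluable still gives 80% in the smaller stratum. That is a best case, because the extra 10% is there to cover losses.

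**Stronger inferences the documents do not support.** A reader might infer that the primary comparison is underpowered. It is not: on the likelier reading, 104 exceeds what the pooled test needs. A reader might infer an arithmetic error, but the sums reproduce. A reader might also infer that the plan sets up misleading separate tests by stratum. With about 81% power in each stratum and the same 2-point effect in both, exactly one would be significant 2 × 0.807 × 0.193 = 31% of the time. But no such tests are planned, so this is a caution for later reporting and not a fault in the plan.

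**Conclusion.** The point holds as an error in the sample-size rationale. The likelier reading is that a base of 52 was doubled to 104 for parity. Stratified randomization does not require that, and the inference offered as the purpose appears nowhere else in the plan.

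At an assumed SD of 2.5, 104 evaluable women give about 98% power pooled. They give about 81% within each stratum only if the strata fill evenly at 52 each, and about 52% for a 2-point interaction. Interaction power stays below 80% across SD 2.0 to 3.0. These figures rest on t-tests, a common SD in all cells and an SD back-solved from the plan's own 26 per arm. The investigators' value may differ.

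The text should be corrected before by-parity results are reported. The validity and power of the primary comparison are not in question.

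**What to change.** **1. Power Calculation.** Replace the sentence giving 52 and the sentence giving 104 with:

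> With SD [investigators' value], 26 evaluable women per arm (52 in total) give 80% power for a 2-point difference at two-sided alpha 0.05. Randomization is stratified by vaginal parity to balance the arms. We retain 104 evaluable women (52 per arm; 114 enrolled), which exceeds the number required for the pooled primary comparison and gives [x]% power for it; the larger size is chosen to allow exploratory estimates by parity. About 80% power within a stratum holds only with 52 evaluable women in that stratum, and the trial is not powered for a treatment-by-parity interaction.

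The SD of 2.5 used in this review should not be copied in as the investigators' value. If 52 per arm was intended, correct the bracketed 26 per arm instead, state the SD, and delete the claim that stratification requires 104.

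**2. Data Analysis.** Add an exploratory linear model of pain at insertion with treatment, vaginal parity and their interaction, reporting the interaction estimate with a 95% CI. State that separate significance tests in each stratum will not be used to claim a difference by parity.

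**3. Only if a within-stratum conclusion is intended.** List it as an aim with its analysis, and state how 52 evaluable women per stratum will be reached, for example by closing a stratum once it is full.

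**Cost.** Steps 1 and 2 need no extra patients or data: one extra model, and a less favourable statement of what the sample supports by parity. Step 3 could lengthen recruitment. At an illustrative 40/60 parity mix, about 52 / 0.40 = 130 evaluable women would have to present to fill the smaller stratum.

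### No single primary test is fixed: the plan offers an unadjusted t-test or Mann-Whitney, chosen from the data, and neither uses the parity strata or baseline pain

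*Combined protocol and SAP*

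**What the plan says.** The analysis plan in section 9 (Data Analysis) is very short. Bivariate comparisons use chi-squared or Fisher's exact test for categorical variables and "t-test or Mann-Whitney for continuous variables depending on the distribution of the data as appropriate". The only sentence specific to the primary outcome is "The primary outcomes will be evaluated per intent-to-treat analysis". It gives the analysis set but no test. No rule for choosing between the two tests is given, and no regression, covariate or stratified test is named.

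Elsewhere the documents say three things that bear on this:

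- **Hypothesis.** Adding buprenorphine "will be associated with lower mean pain scores at time of osmotic dilator insertion" (section 9, Primary Hypothesis; the primary aim in section 6 also concerns the mean).
- **Stratification.** Randomization uses blocks of 4 and 6 within two vaginal-parity strata (section 9, Randomization). The reason given is that "vaginal parity may affect pain at the time of osmotic dilator insertion" (section 9, Power Calculation). The same part raises the total to 104, or 52 per stratum, "to see a difference between strata per group".
- **Baseline pain.** A pre-procedure NRS score is collected (section 9, Outcomes and Schedule of Assessments).

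**The concern.** There are three separate weaknesses.

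1. **The primary result is not fixed in advance.** The t-test compares means. Mann-Whitney compares the tendency of one arm to score higher than the other. Choosing between them after seeing the distribution means that the data decide which question is answered, and the answer may not be the mean difference in the hypothesis.
2. **Design and analysis do not match.** Stratified randomization balances parity between arms. If parity is prognostic, a pooled test that ignores it still counts the between-stratum variation as noise, so its standard error is too large.
3. **Baseline pain is collected but not used.** This costs precision only. The unadjusted standard error remains valid.

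**Working it through.** **Inputs from the documents.** Two-sided alpha 0.05, 80% power, a 2-point difference, 26 per arm as the base size, 104 in total over two parity strata of 52, and 1:1 allocation.

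**Not in the documents.** The SD, the effect of parity on pain, and the correlation of baseline with insertion pain. These are assumed below.

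**Reproducing the plan's figure.** With no SD stated, the calculation can only be run backwards. In the normal approximation, n per arm = 2(1.96 + 0.842)²·SD²/δ². With n = 26 and δ = 2, SD² = 26 × 4 / 15.70 = 6.62, so SD = 2.57. The t-based version gives 2.52. I use 2.5 as the main case and 3.5 as a high one.

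**Effect of ignoring parity.** Let d be the difference in mean pain between two equal strata. Within-stratum SD = √(6.25 − d²/4). The unadjusted standard error is too large by the factor 2.5 / within-stratum SD, and the actual type I error is 2[1 − Φ(1.96 × factor)].

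| d | Within-stratum SD | Factor | Type I error |
|---|---|---|---|
| 1 | 2.449 | 1.021 | 0.0455 |
| 2 | 2.291 | 1.091 | 0.0325 |

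The test is therefore conservative. Simulation of the planned randomization gave 0.046–0.047 and 0.030–0.034 unadjusted, against 0.049–0.053 adjusted.

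**Adding baseline pain.** With within-stratum correlation ρ, residual SD = within-stratum SD × √(1 − ρ²). For ρ = 0.3 this is 2.449 × 0.954 = 2.34 (d = 1) or 2.291 × 0.954 = 2.19 (d = 2).

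**Power.** Simulated with 104 women, alternating blocks of 4 and 6 within stratum, and 10,000 runs per setting (6,000 for SD 3.5). The unadjusted t-test is compared with a linear model containing parity and baseline.

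| SD | Effect | d | ρ | Unadjusted | Adjusted |
|---|---|---|---|---|---|
| 2.5 | 2 | 0 | 0 | 98.1% | 98.0% |
| 2.5 | 2 | 1 | 0 | 98.3% | 98.4% |
| 2.5 | 2 | 1 | 0.3 | 98.2% | 98.9% |
| 2.5 | 2 | 2 | 0.3 | 98.7% | 99.6% |
| 2.5 | 1.4 | 0 | 0 | 80.6% | 80.1% |
| 2.5 | 1.4 | 1 | 0 | 81.3% | 81.9% |
| 2.5 | 1.4 | 1 | 0.3 | 81.3% | 85.4% |
| 2.5 | 1.4 | 2 | 0.3 | 82.5% | 89.5% |
| 3.5 | 2 | 0 | 0 | 81.9% | 81.4% |
| 3.5 | 2 | 1 | 0.3 | 83.2% | 86.6% |
| 3.5 | 2 | 2 | 0.3 | 83.8% | 88.7% |

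**Interval width (SD 2.5).** The mean 95% CI width is 1.94 unadjusted. Adjusted, it is 1.82 (d = 1, ρ = 0.3; 6% narrower), 1.70 (d = 2, ρ = 0.3; 12% narrower) or 1.95 (d = 0, ρ = 0; about 0.5% wider).

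**Bounded scores.** Rounding and cutting scores to 0–10 leaves the picture unchanged. For a 1.4-point effect and ρ = 0.3, power is 80.3% against 83.9% (d = 1) and 81.1% against 88.1% (d = 2).

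**Choice of test.** Always taking the smaller of the two p-values gives a null rejection rate of at most about 0.057 when parity has no effect, so error inflation is small. The change of question can be larger. In one constructed pair of NRS distributions, both with mean 6.0 but with probability 0.66 of a higher score in one arm (ties counted half), 52 per arm gave 5.8% rejection by t-test and 80% by Mann-Whitney. That example shows what is possible and does not forecast this trial.

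**The case against.** The strongest counter-argument starts from the sample size. The plan needs 52 women for a two-arm comparison and then asks for 52 in each parity stratum. The natural arithmetic reading is a separate comparison within each stratum. If so, parity is already handled, and the pooled figures above do not apply. This stands as a possibility, but no by-stratum or interaction analysis is described, so the plan needs a sentence either way.

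The precision gain is also modest and rests on assumptions. Parity alone at d = 1 narrows the interval by about 2% (2.449/2.5 = 0.98), so most of the 6% comes from the assumed correlation. That correlation may be low: section 9 excludes women with chronic pain conditions, sections 9 and 10 exclude recent narcotic use, and baseline is scored before anything is done. The 12% figure needs a parity difference as large as the treatment effect the trial calls clinically meaningful. At 2 points and SD 2.5, adjustment barely changes power. All of this is correct.

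Finally, with identical distributions in the two arms both tests are valid, and using Mann-Whitney does not prevent the mean difference from being reported. But the plan does not commit to reporting it, so the gap in prespecification remains.

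**Conclusion.** The concern holds. The plan does not say which test or which effect measure is the primary result, one of its two candidate tests does not address the stated hypothesis, and no described analysis uses the stratification factor or the baseline score.

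This does not endanger a pooled primary comparison. The unadjusted t-test is unbiased, its type I error is at or below nominal, and 52 per arm keeps at least 80% power for 2 points up to an SD of about 3.6. The main harm is ambiguity about the primary result. The secondary harm is a wider interval and less power for effects below 2 points, or for 2 points if the SD is near 3.5. Its size depends on a parity effect and a baseline correlation that the documents do not give, and it is nil if neither factor is prognostic.

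**What to change.** First state whether the primary comparison is pooled across parity strata or made within each stratum. If it is pooled, replace the choice of tests for the primary outcome in Data Analysis with wording such as:

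> NRS at osmotic dilator insertion will be compared by a linear model with terms for treatment, vaginal-parity stratum and baseline NRS, in all randomized women by assigned arm. The adjusted mean difference with 95% CI and two-sided p-value is the primary result.

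Use the same model for the 2-hour score. Keep a parity-stratified rank test (van Elteren) as a sensitivity analysis only. Add a sentence on how missing insertion or baseline scores are handled. A term for study site is optional, because randomization is not stratified by site.

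If within-stratum comparisons are intended, say so and name the test and effect measure for each stratum.

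The cost is one paragraph, with no new data and no extra patients. If neither covariate predicts pain, the interval is about 0.5% wider.
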